7.2 Demographics and Baseline Characteristics

The descriptive summaries of subjects' demographic and baseline characteristics are presented for the Safety, ITT, and PP populations.

Subject characteristics include a summary of the following:

- Subject demographics
- Baseline characteristics
- Pre-existing medical conditions

Continuous variables are summarized using number of observations, mean and standard deviation, median, and minimum and maximum values. Categorical values are summarized using number of observations and percentages.

Medical History and AEs will be summarized by MedDRA System Organ Class and preferred term.

7.3 Treatment Compliance and Exposure

Exposure summary by treatment group will be presented for the Safety and PP populations. The distribution of subjects by the total number of weeks on therapy (baseline, 8, 10, and 12) will be presented. For the Safety population, the summary of exposure will be based on the actual treatment received.

Treatment compliance is defined as the number of wound treatment doses (KB103 and placebo) received divided by the number of doses expected, ($\times 100$) over the time period defined by the first and last treatment dose dates. Descriptive statistics for treatment compliance and the number and percentage of subjects at least 90% compliant will be presented by treatment group for the ITT, Safety, and PP populations.

8 Efficacy (Proof of Mechanism) Analyses

The study has a complete randomized-block design in which each subject serves as a block to receive all of the treatment conditions. The Phase I/II studies provided at least one pair of target wounds, with one wound being treated with placebo and one wound being treated with KB103. Efficacy measurements are taken multiple times (or repeatedly) over the on-treatment period and off-treatment period from each subject.

All data will be presented using summary statistics or frequency tables, as appropriate, and will be analyzed for superiority comparisons between KB103 and placebo treatments. The description of the sample will be done using summary statistics (n, mean, standard deviation, median, and maximum/minimum) for continuous data and using frequency statistics (counts and percentages) for categorical data. Hypothesis testing, unless otherwise indicated, will be performed at the 5% significance level (1-sided). All P-values will be rounded to four decimal places; P-values less than 0.0001 will be presented as '<0.0001' in all tables. Unless specifically stated, all confidence intervals will be two-sided with 95% coverage.

Efficacy measures collected pre-dosing will be considered as the baseline measurement (defined in [Section 6.2](#)) in this study. For all efficacy analyses, subjects will be analyzed in the group to which they were randomized.

The Sponsor, or their designee, will analyze the data using SAS® Statistical Analysis System Version 9.3 or higher.

8.1 Wound Efficacy Analyses:

8.1.1 Change in Wound Surface Area:

The efficacy analyses will be based on the observed ITT population.

The efficacy objective is the proportion of DEB wound sites with complete wound healing from baseline ($\geq 90\%$ reduction in wound surface from baseline) in KB103 versus placebo treated intra-participant wound sites at Weeks 8, 10 and 12 as determined by the Investigator.

The number and percentage of subjects in each treatment group defined as Complete Wound Healing (CWH) will be tabulated. The null and alternative hypotheses are as follows:

Null Hypothesis $H_0: \%CWH \text{ in KB103} = \%CWH \text{ in Placebo}$

Alternate Hypothesis $H_1: \%CWH \text{ in KB103} > \%CWH \text{ in Placebo}$

Where $\%CWH$ is the percentage of wounds with a complete wound healing from baseline at week 8, 10 and 12. A one-sided significance level of 0.05 is considered

The objective of the proportion of DEB wound sites with complete wound healing from baseline ($\geq 90\%$ reduction in wound surface from baseline) will be analyzed using the Cochran-Mantel-Haenszel (CMH) test stratified by the time points (weeks 8, 10 and 12). Under the null hypothesis of no association between complete wound healing and treatment, this test statistic follows a chi-square distribution with 1 degree of freedom. The CMH test provides test of independence for the repeated evaluations at weeks 8, 10 and 12.

In addition to testing the null hypothesis, the CMH test also provides an estimate of the common odds ratio to summarize how large the treatment effect is when pooled across the different weeks of the treatment assuming the odds ratio is the same in the different weeks of treatment. This assumption will be tested using the Breslow-Day test and corresponding p-values will be provided. The null hypothesis of the CMH test is that the odds ratios within each week are equal to 1, indicating the complete wound healing proportions are the same.

A summary table with individual treatment proportions and the p-values treatment effect resulting from the chi-square test will be provided. In addition, p-values for independence of weekly evaluations (weeks 8, 10 and 12) using the Breslow-Day test will be provided.

8.1.1.1 Sensitivity and Supplemental Analyses of the Change in Wound Surface Area:

- The analysis performed in Section 8.1.1 for the efficacy objective will be repeated for the PP and LOCF imputed ITT populations.
- The analysis performed in Section 8.1.1 for the efficacy objective will be repeated for weeks 8, 10 and 12, separately with and without stratification by time points for observed, PP and LOCF imputed ITT populations.

Other Analyses of the Change in Wound Surface Area for observed and LOCF imputed populations Include:

- The analysis performed in Section 8.1.1 for the efficacy objective will be repeated for wound healing with $\geq 50\%$ reduction in wound surface from baseline with and without stratification by time points.
- The analysis performed in Section 8.1.1 for the efficacy objective will be repeated for wound healing with $\geq 75\%$ reduction in wound surface from baseline with and without stratification by time points.

- The analysis performed in Section 8.1.1 for the efficacy objective will be repeated for wound healing with 100% reduction in wound surface with and without stratification by time points.

All the efficacy wound healing responses will be summarized by treatment and timepoints for observed and LOCF imputed ITT populations. The percent reduction in wound surface from baseline will be summarized descriptively by treatment and timepoints and treatment comparisons will be performed using the Wilcoxon rank-sum test for observed and LOCF imputed ITT populations. A subject listing will be provided for these reductions in wound surface.

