2.2 Study Objectives Phase II

2.2.1 Primary

- 8) To assess wound closure through post-administration imaging:
 - a. To assess proportion of complete wound closure of B-VEC treated wounds to that of placebo treated wounds at weeks 8, 10 and 12.
 - b. Time to wound closure of a KB103-administered wound relative to a placebo-administered wound
 - c. Duration of wound closure of a KB103-administered wound relative to a placebo-administered wound

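### Three Phase II primary objectives are each tested at a default one-sided 5% with no ranking, order or success rule, so the chance of at least one false success is about 8% to 14%

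*SAP*

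**What the plan says.** SAP 2.2.1 places three items under one Phase II primary heading, without ranking:

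- (a) "To assess proportion of complete wound closure of B-VEC treated wounds to that of placebo treated wounds at weeks 8, 10 and 12"
- (b) how quickly wounds close on KB103, compared with placebo
- (c) how long closure then lasts, again compared with placebo

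SAP 8 plans superiority comparisons and sets the level for all of them: "Hypothesis testing, unless otherwise indicated, will be performed at the 5% significance level (1-sided". SAP 8.1.1 repeats it for the healing proportion: "A one-sided significance level of 0.05 is considered". Sections 8.1.2 and 8.1.3 compare time to closure and duration of closure by analysis of variance, each on observed and on LOCF-imputed ITT data. SAP 8.2 takes only the collagen VII and anchoring fibril objectives out of formal testing.

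One analysis is given some prominence. SAP 8.1.1 states: "The efficacy objective is the proportion of DEB wound sites with complete wound healing from baseline". It defines healing as a reduction of at least 90%, writes the only null and alternative hypotheses in the plan, names a week-stratified CMH test, and fixes the data set: "The efficacy analyses will be based on the observed ITT population".

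Neither the SAP nor Protocol section 10 states a testing order, a multiplicity adjustment or a rule for what counts as success.

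**The concern.** If three objectives are all primary, each is tested at 5%, and nothing says which result decides, a favourable result on any one could be presented as meeting a primary objective. The 5% then describes each test on its own, not the claim that the trial succeeded.

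Two features of this plan make that more than a formality. First, SAP 1 says that the plan was prepared after an initial partial analysis in a study that was not blinded, so the decisive result could be chosen with some data in view. Second, the choice is open even within an objective. Time and duration each have two co-equal data sets. For the healing proportion, SAP 6.3 says that missing primary endpoints are filled by the last observed value, while 8.1.1 rests on observed data.

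**Working it through.** The documents state no family-wise error rate, so there is no figure of the plan's own to reproduce. The check asks what the stated per-test level implies.

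**Inputs**

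- Level per test: 0.05, one-sided (SAP 8 and 8.1.1).
- Number of primary comparisons: 3 (SAP 2.2.1, tested in 8.1.1, 8.1.2 and 8.1.3).
- Correlation between the three test statistics: not given anywhere. It is assumed here and shown as a range.

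**Step 1. Independent tests.** Chance of at least one false success = 1 − 0.95³ = 14.3%. The Bonferroni ceiling, whatever the correlation, is 3 × 0.05 = 15%.

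**Step 2. Correlated tests.** The three endpoints come from the same wounds, so positive correlation is likely. With a common correlation ρ between normal test statistics and z = 1.645, the chance is 1 − ∫ φ(x) · Φ((z − √ρ·x)/√(1 − ρ))³ dx:

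| Assumed ρ | At least one false success |
|---|---|
| 0 | 14.3% |
| 0.3 | 13.0% |
| 0.5 | 11.8% |
| 0.7 | 10.3% |
| 0.9 | 8.0% |

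**Step 3. If the ANOVAs are not one-sided.** An ordinary F-test has no direction, and SAP 8.1.2 and 8.1.3 do not say how a one-sided p-value would be obtained. Run as usual 5% F-tests, each has a 2.5% chance of a false result in favour of KB103. With independence: 1 − 0.95 × 0.975² = 1 − 0.95 × 0.9506 = 9.7%.

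**Step 4. Check by simulation.** Null data were simulated for 12 subjects with paired wounds: 4,000 runs in each of five scenarios, with assumed within-subject and serial correlation. At least one of the three primary tests was significant in about 11% to 18% of runs. Part of that excess is not multiplicity. The CMH test alone rejected in about 6% to 11% of runs, because it treats repeated weeks on the same wounds as independent strata. That is a separate matter, and it is why the 8% to 14% range, which assumes that each test holds its own level, is the one used here.

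**The case against.** The strongest reply is that the SAP already has a lead analysis. Section 8.1.1 speaks of the efficacy objective in the singular and gives it the only written hypotheses, a restated level, one named test and one data set. Most of the repeats are headed sensitivity, supplemental or other. The study is a pilot without a sample size calculation, its efficacy section is framed as proof of mechanism, and a Phase 3 trial is to follow.

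Much of this stands. A reader might infer that the plan has no lead test at all; 8.1.1 does not support that. What is missing is narrower: a statement that this test ranks above time to closure and duration, which 2.2.1 also calls primary.

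A reader might also add up every planned comparison and quote a far larger error rate. One reading gives 1 + 2 + 9 + 3 + 12 + 6 + 2 + 2 = 37 tests: the main CMH; PP and LOCF; three weeks in three data sets; unstratified in three data sets; three other thresholds, two ways, in two data sets; weekly rank-sum tests in two data sets; time; duration. The documents do not support this as a headline, for two reasons.

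- The count is not fixed. SAP 8.1.1.1 asks for repeats "separately with and without stratification by time points for observed, PP and LOCF imputed ITT populations", which can be read several ways, and the rank-sum test is not clearly weekly. The total runs from 1 + 2 + 3 + 12 + 2 + 2 + 2 = 24 to 1 + 2 + 18 + 12 + 6 + 2 + 2 = 43.
- The repeats largely re-test the same hypothesis on the same wounds. For 37 tests, the error rate moves from 85% to 43% to 16% as an assumed common correlation goes from 0 to 0.5 to 0.9, and nothing in the documents fixes that value.

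Pilot status excuses the absence of a power calculation. It does not explain why a plan that specifies superiority tests at a stated level leaves its primary objectives unranked.

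**Conclusion.** The point holds in a limited form. Three Phase II primary objectives are tested at a default one-sided 5%, with no ranking, order, adjustment or success rule, and two of them have no main data set. The chance of at least one false success is about 8% to 14% for assumed correlations of 0.9 to 0, or about 10% with independence and two-sided F-tests. These figures assume that each test holds its nominal level and that the correlation is common to all pairs. The documents supply neither a correlation nor evidence that the level is held.

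It would go too far to say that a false claim will be made: neither document states a success rule or a confirmatory claim. This is a worthwhile, inexpensive clarification for a pilot, not a flaw that invalidates the trial.

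**What to change.** In SAP 8, add text to this effect:

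1. The ≥90% healing comparison in 8.1.1, on observed ITT, is the decisive test.
2. Time to closure (8.1.2) and then duration of closure (8.1.3), each on observed ITT, are tested formally only if the preceding test succeeds, each at the full level.
3. Every other p-value in 8.1.1.1 to 8.1.3, including the LOCF, PP, by-week and other-threshold repeats, is nominal and descriptive.
4. Because the SAP was written after a partial analysis, this order limits selective claims but does not guarantee a 5% error rate.

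Item 4 matters because a reader might infer that a fixed order restores the 5% level. An order set after data have been seen cannot promise that.

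The cost is SAP wording only: no new data and no more subjects. The downside is that no formal claim can be made on a later endpoint if an earlier one fails.

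### The main healing test stratifies by week alone, so it counts each wound up to three times, ignores the subject block, and has no known one-sided 5% level

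*SAP*

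**What the plan says.** SAP section 8 describes the layout correctly: "The study has a complete randomized-block design in which each subject serves as a block to receive all of the treatment conditions". It adds that "Efficacy measurements are taken multiple times (or repeatedly) over the on-treatment period and off-treatment period from each subject". Section 8.1.1 defines complete healing as at least 90% reduction in wound surface and counts it per wound. It states that healing "will be analyzed using the Cochran-Mantel-Haenszel (CMH) test stratified by the time points (weeks 8, 10 and 12", and that under the null "this test statistic follows a chi-square distribution with 1 degree of freedom", at a one-sided level of 0.05. The same section says "The CMH test provides test of independence for the repeated evaluations at weeks 8, 10 and 12" and that "p-values for independence of weekly evaluations (weeks 8, 10 and 12) using the Breslow-Day test will be provided".

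Section 8.1.1.1 has the analysis "repeated for weeks 8, 10 and 12, separately with and without stratification by time points" as supplementary work. For percent reduction in wound surface, "treatment comparisons will be performed using the Wilcoxon rank-sum test for observed and LOCF imputed ITT populations". Section 8 names no subject stratum, cluster-robust variance, random effect or permutation reference. Section 8.1.1 does not use the word primary, but SAP 2.2.1 lists this comparison as the first Phase II primary objective.

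**The concern.** The CMH reference distribution requires independent units within and across strata. Here a wound that heals by week 8 and stays healed adds the same information three times, while the variance formula treats it as three separate wounds. Separately, the KB103 and placebo wounds of one patient share that patient, and the test gives no credit for the pairing. The two faults pull in opposite directions, so the p-value may be too small or too large and the reader cannot tell which from the test itself.

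The Breslow-Day test does not settle this. It compares odds ratios between weeks and says nothing about whether the weekly evaluations are independent. At stake is the p-value for the first Phase II primary objective, in a plan that SAP section 1 says was written after a partial analysis of unblinded data.

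**Working it through.** **Inputs from the documents.** One-sided alpha is 0.05, so the critical value is z = 1.645 (SAP 8.1.1). Strata are weeks 8, 10 and 12. SAP 4.1 gives up to 12 subjects. From the version table in SAP section 3, 2 subjects have one KB103 and one placebo wound. The other 10 are taken as having two KB103 and one placebo wound. That gives 2×1 + 10×2 = 22 KB103 wounds and 12 placebo wounds.

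**Assumptions (not in the documents).** Healing is 35% in both arms. rho is the correlation of one wound's healed status between weeks. c is the correlation between different wounds of the same subject, taken as equal for all pairs of weeks.

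**The plan's own figure.** With all wound-weeks independent, the asymptotic level is 5%. Simulation of this layout gives 4.5%, and 4.6–5.2% over healing rates of 20–60% with 12 or 14 subjects. The stated level is therefore reproduced only when the repeats are independent.

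**Closed form.** Let v be the variance of one healed/not-healed result.

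- The variance of a wound's three-week total is 3(1+2·rho)v. CMH assumes 3v.
- The covariance between the totals of two wounds in one subject is 9cv. CMH assumes 0.
- For a subject with k KB103 wounds and one placebo wound, the KB103 mean minus the placebo value has variance (1+1/k)·3(1+2·rho)v + [(k−1)/k − 2]·9cv.
- Since (k−1)/k − 2 = −(1+1/k), the ratio of true to assumed variance is 1 + 2·rho − 3c for k = 1 or 2.
- The level is 1 − Φ(1.645/√(1 + 2·rho − 3c)).

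Mixing the two wound layouts shifts this slightly. The simulation (latent-normal model, 40,000 runs per cell) allows for that.

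| rho | c | variance ratio | closed-form level | simulated level |
|---|---|---|---|---|
| 0.3 | 0 | 1.6 | 9.7% | 9.3% |
| 0.3 | 0.2 | 1.0 | 5.0% | 5.0% |
| 0.5 | 0 | 2.0 | 12.2% | 11.8% |
| 0.5 | 0.2 | 1.4 | 8.2% | 8.2% |
| 0.5 | 0.33 | 1.01 | 5.1% | 5.2% |
| 0.8 | 0 | 2.6 | 15.4% | 15.1% |
| 0.8 | 0.3 | 1.7 | 10.4% | 10.6% |
| 0.8 | 0.53 | 1.01 | 5.1% | 5.4% |
| 0.8 | 0.8 | 0.2 | 0.01% | 0.2% |

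With full persistence (rho = 1, c = 0) the limit is 1 − Φ(1.645/√3) = 17.1%. The level returns to 5% where 2·rho = 3c, that is c = 2·rho/3. Healing rates of 20% or 50% move the simulated values by at most 1 point. A continuity correction does not cure the inflation (up to 13.4%).

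**Separating the two faults.** One week tested alone, without the subject, gives 5.1–5.3% at c = 0 and 2.6–2.7% at c = 0.3. Ignoring the block is conservative, so the inflation comes from repetition.

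**Worked example (invented counts, status unchanged over the weeks).** Take 12 of 22 KB103 and 4 of 12 placebo wounds healed. The expected KB103 count is 16×22/34 = 10.353. The variance is 22×12×16×18/(34²×33) = 1.993. So z = (12 − 10.353)/√1.993 = 1.167 and one-sided p = 0.122. Three identical strata give z = 1.167×√3 = 2.021 and p = 0.022, from the same 34 wounds.

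**The case against.** - **Direction.** The net bias is not determined. Wounds of one patient share the patient and the mutation, and protocol 6.3 asks for similar locations, so c near 0 is the unfavourable end of the range. This stands. The claim is that the level is unknown and can be inflated, not that it must be.
- **Three entries per wound.** The SAP schedules have no visit near week 10 (about Day 70) in versions 2.2 or 3.1, and version 1.0 images at Days 42 and 84. If week 10 is missing in 2.2 and 3.1, and version 1.0 also lacks week 8, the level is about 9% at rho 0.5, c 0 and about 11% at rho 0.8, c 0. It drops to 5.7% at rho 0.5, c 0.2. Inflation is smaller but remains. The SAP plans all three weeks, and home imaging about twice a week could supply week 10.
- **Reading the chi-square literally.** Rejecting above 3.84 in the right direction gives 8.3% at rho 0.5, c 0 and 5.0% at c 0.2. That rule is nominally a 2.5% test, so it is inflated as well. The SAP does not say which rule applies.
- **Single-week repeats.** These would expose a pooled result that no single week supports. They are supplementary, no week is named, and they still ignore the subject. The pooled repeats without stratification keep the repetition.
- **Wording.** The CMH sentence may mean independence of treatment and healing, which CMH does test, and the SAP elsewhere states the role of Breslow-Day correctly. Only the later Breslow-Day sentence is plainly wrong.
- **Pilot status.** No sample size was calculated, but section 8 still sets hypotheses, an alpha and superiority p-values.

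**Conclusion.** The concern holds. As written, the test contradicts the block design stated in the same SAP section, and its 5% level cannot be relied on. For 12 subjects and 35% healing, the one-sided error is about 9–15% when c is near 0 and rho is 0.3–0.8. It is near 5% at c = 2·rho/3 and lower beyond that. These figures assume that each wound is observed at all three weeks and that the one-sided test rejects at z > 1.645. All correlations and healing rates are assumptions. LOCF, used in the sensitivity analyses, copies values forward and so tends to raise rho. The rank-sum test also ignores pairing, which mainly costs precision. This should be corrected before the p-value is used.

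**What to change.** - **Main test.** Use a one-sided within-subject permutation test on each wound's healing total over weeks 8, 10 and 12 (mean of the observed weeks if one is missing). It uses each wound once, and it avoids choosing a week after the partial analysis.
- **Permutation set.** Permute only among wounds that could have received either product. Under protocol 6.3 a third area in version 4.0 goes only to KB103. State the assignment rule for each protocol version, because the test rests on it.
- **Alternative.** Use an exact CMH stratified by subject at one named week. This also keeps an odds ratio as the effect estimate.
- **One-sided p-value.** State that it comes from the signed statistic.
- **Percent reduction.** Replace the rank-sum test with a signed-rank test on the within-subject difference (mean of the KB103 wounds minus the placebo wound).
- **Wording.** Remove the statements that CMH or Breslow-Day tests independence of the weekly evaluations. Keep Breslow-Day for homogeneity of odds ratios only.

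**Cost.** SAP text and modest programming, with no new data. With so few subjects the permutation test is conservative: its simulated error at nominal 5% was between 2.1% and 4.2% over the settings run. The p-value may be less favourable than the planned one. Simulated power at an assumed 70% versus 35% healing is 73–87% for the permutation test and 49–59% for the one-week exact CMH. At 80% versus 30% it is 96–99.5% and 82–90%.
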